#### If after a 1 week rest:

• The patient meets the above criteria for treatment, the patient may receive HCW9218. The patient calendar would be adjusted (reset) and the patient returns in 3 weeks for the next course of treatment.

• The patient does not meet the above criteria for treatment or the Investigator feels holding treatment would be of benefit to the patient, the dosing may be skipped. The patient would return for reassessment at the time of next planned dose (i.e. in 3 weeks). A decision is made at that time whether to treat or discontinue HCW9218 permanently. If Cycle 2 cannot be given (is skipped) due to treatment related toxicity, a DLT event must be reported.

Refer to Section 6.3 for additional information regarding DLTs.

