### **STAGE 2 Continual Reassessment Method (CRM)**

The study design changes to an application of the continual reassessment method (CRM). Enrollment occurs in cohorts of 3. Within a 3 patient dose cohort, a minimum of 14 days must separate the 1st and 2nd patient with no staggering of enrollment required between and 2nd and 3rd patient. Once the 3rd patient in a cohort reaches Day 21 (DLT period), a new cohort of 3 patients is sequentially assigned to the most appropriate dose by the study statistician based on the updated toxicity probabilities. The goal will be to identify one of the 4 dose levels corresponding to the desired maximum toxicity rate of ≤25%. The MTD will be identified by the minimum of the following criteria: (1) the total Stage 2 sample size of 24 is exhausted or (2) 9 consecutive patients are enrolled at the same dose.

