### 6.3 Monitoring for Dose Limiting Toxicities and Excessive Toxicity

Toxicity and adverse events are classified and graded according to NCI's Common Terminology Criteria for Adverse Events V 5.0 (CTCAE) unless otherwise noted in Section 10.

Note during the fast-track dose escalation only (Stage 1, Step 1), patients also are monitored for the pre-defined treatment emergent events defined in Section 6.2.1.

**Dose Limiting Toxicity (DLT)** is defined as any of the following treatment emergent adverse events using the NCI Common Terminology Criteria for Adverse Events (CTCAE) Version 5.0 within the 21 days after the 1st dose of HCW9218:

DLT event	Exceptions:		
Any Grade 3 or Grade 4 febrile neutropenia Any Grade 3 thrombocytopenia with bleeding Any Grade 3 or higher non-hematologic adverse event	
 
Grade 4 lymphopenia hat resolves to Grade 1 or lower (or to Baseline or lower, if pre-existing Grade 2 or higher) within 7 days
 
Grade 4 leukopenia that resolves to Grade 1 or lower (or to Baseline or lower, if pre-existing Grade 2 or higher) within 7 days
 
Grade 3 nausea, vomiting and/or diarrhea that last < 72 hours
 
Grade 3 or higher electrolyte abnormality that lasts < 72 hours, is not clinically complicated, and resolves spontaneously or responds to conventional medical interventions
 
Isolated Grade 3 elevation of ALT and/or AST that resolves to Grade 1 or lower (or to Baseline or lower, if pre-existing Grade 2 or higher) within 7 days
 
Grade 3 amylase or lipase that is not associated with symptoms or clinical manifestations of pancreatitis
 
		
	
 
Grade 3 fatigue, not due to disease progression, that lasts < 1 week
 
		
Hy's Law case (i.e., alanine aminotransferase/ aspartate aminotransferase (ALT/AST) >3 x ULN in combination with total bilirubin level (TBL) > 2 x ULN in the absence of cholestatic injury (ALP < 2 x ULN (Ricart, 2017; FDA, 2009)) and no other cause identified) after excluding biliary tract obstruction and liver metastasis  Inability to receive Cycle 2 dosing due to treatment related toxicity	MORE - I WOR		

The Dose Limiting Toxicity (DLT) Observation Period is defined as 21 days after the first dose of HCW9218. The DLT period does not end until the patient is assessed on Cycle 2 Day 1 (+3 days) and the results of lab work drawn on Cycle 2 Day 1 (+3 days) confirms no new DLTs since the previous assessment.

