2. Safety labs can be collected up to 72 hours prior to administration of HCW9218 except for C2 D1 where labs cannot be collected sooner than Cycle 1 Day 22 / Cycle 2 Day 1 (the end of DLT period).

3. C1D1 and C2D1: Vital signs (body temperature, heart rate, respiratory rate, systolic and diastolic blood pressure) are documented before each HCW9218 dose and then after dosing at 15 min (± 5 min), 30 min (± 5 min), 60 min (± 10 min) and 120 min (± 15 min) then hourly (± 15 min) until discharge from the clinic or at completion of dose monitoring.

4. For C3D1 and subsequent doses: Vital signs (body temperature, heart rate, respiratory rate, systolic / diastolic blood pressure) are documented before each HCW9218 dose and then after dosing at 15 min (± 5 min) and 30 min (± 5 min).

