## 10.2 Event Monitoring and Documentation

Event monitoring and documentation begins at the time of the 1st HCW9218 dose and continues through the End of Treatment visit. Active monitoring for adverse events ends with the End of Treatment visit unless there are ongoing study related toxicity. After the EOT through 12 months from Cycle 1 Day 1 (follow-up for response and survival), events are documented upon knowledge. Refer to the table below:

Event	Active Treatment Period		During follow-up for
	Cycle 1 Day 1 through	Cycle 2 Day 1 through	12 months from
	the end of DLT	though End of	Cycle 1 Day 1
	observation period and	Treatment (EOT) visit	(events are
	the DLT assessment is		documented upon
	completed		knowledge)
Any event meeting the definition of serious	X	X	X 1
regardless of attribution or expectedness	^	Λ	^
Any death (date and cause)	Χ	Χ	Χ
1st incidence of a pre-defined adverse event	X 		
during Fast-track enrollment per Section 6.2.1	Λ-		
Any event meeting the definition of a Dose	X3		
Limiting Toxicity (DLT)	Λ'		
All ≥Grade 2 AEs regardless of attribution (see	X	X	
exceptions in Section 10.2.1)	^	^	
Targeted Toxicity Worksheet (Appendix IV) –	X (refer to schedule in		
record all AE grades	Section 10.2.2)		

- 1. Events are documented upon knowledge if they are unexpected and at least possible related to HCW9218.
- 2. Used only once to trigger change from 1 patient cohort to 3 patient cohort and move to Stage 1 Step 2 or Stage 2 (if a DLT also occurs).
- 3. Stage 1: Any event meeting the definition of DLT is in association with the 1st treatment cycle (through the end of the DLT period) is also be reported as a DLT event contributing to subsequent dose cohort decisions per Section 12. Stage 2 (CRM component) event Section 13.4.

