- Cohort 4 is completed without a pre-defined AE or a DLT neither Step 2 nor Stage 2 is used if a total of 9 patients are enrolled in Cohort 4 to complete the study.

Stage 2 is initiated at the 1st DLT. The study design changes to an application of the continual reassessment method (CRM) with an informative skeleton based on constrained maximum likelihood estimation (lasonos & O'Quigley, 2012). Enrollment occurs in cohorts of three patients. Each new cohort of three patients are sequentially assigned to the most appropriate dose by the study statistician based on the updated toxicity probabilities once the 3rd patient in a cohort reaches Day 21 (DLT period). The goal will be to identify one of the 5 dose level strategies corresponding to the desired maximum toxicity rate of ≤25%. The MTD will be identified by the minimum of the following criteria: (1) the total Stage 2 sample size of 24 is exhausted or (2) 9 consecutive patients are enrolled at the same dose. The function 'crm' from the R package 'dfcrm' will calculate posterior means of toxicity probabilities. Dose escalation of more than one level is not permitted with this design.

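### A Cycle 2 skipped for treatment-related toxicity is a DLT, but it can be declared only on Day 29 to 32, and no rule makes the next dose decision wait for it

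*Combined protocol and SAP*

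**What the plan says.** The DLT list in Section 6.3 and the Schema includes one item tied to the second dose: "Inability to receive Cycle 2 dosing due to treatment related toxicity". Section 6.1.1 says how that item arises. A dose may be held for up to one week for any related toxicity still present, with no grade floor. After the rest there are two outcomes. Either the patient meets the criteria and may be dosed, or the criteria are not met or "the Investigator feels holding treatment would be of benefit to the patient, the dosing may be skipped". For Cycle 2 it adds: "If Cycle 2 cannot be given (is skipped) due to treatment related toxicity, a DLT event must be reported".

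DLTs are defined within 21 days of the first dose. On the close of the period, Section 6.3 says: "The DLT period does not end until the patient is assessed on Cycle 2 Day 1 (+3 days"). A footnote to the Section 8.1 schedule fixes that visit in calendar terms: "labs cannot be collected sooner than Cycle 1 Day 22 / Cycle 2 Day 1 (the end of DLT period").

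The Stage 2 dose decision has its own clock. The Synopsis says: "Once the 3rd patient in a cohort reaches Day 21 (DLT period), a new cohort of 3 patients is sequentially assigned". Section 13.1 likewise assigns each cohort from "updated toxicity probabilities once the 3rd patient in a cohort reaches Day 21 (DLT period"). In Stage 1 Step 1, patients are separated by at least 21 days (6.2.1). Footnote 3 to the Section 10.2 table describes the DLTs that feed cohort decisions as those "in association with the 1st treatment cycle (through the end of the DLT period").

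**The concern.** The plan requires a certain event to be counted as a DLT, yet it sets the DLT window and the dose-decision day so that the event can arrive after both. The DLT count determines the MTD, which is the primary endpoint, and the first DLT opens Stage 2. A team following the text exactly could assign a cohort, or dose the next single patient one level higher, without a DLT that the same text says must be reported. The protocol does not say how such a late DLT enters a decision already made, and the wording in 10.2 could be read as leaving it out.

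Only toxicity below the grade-based thresholds is affected. A Grade 3 non-hematologic event, for example, counts on its own terms.

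There is also a smaller gap. The Cycle 2 item has no day limit in 6.3 or the Schema, the skip is permissive, and 6.1.4 allows medically necessary schedule changes without a deviation. A Cycle 2 dose given after the hold has run out, with no skip declared, has no stated DLT status.

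**Working it through.** **Days for one patient** (Schema, 6.1.1, 6.3, 8.1)

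- Cycle 2 Day 1: 1 + 21 = Day 22, which reproduces the Schema's assessment day. With the +3-day window it is Day 22 to 25.
- End of a one-week hold: 22 + 7 = Day 29, up to 25 + 7 = Day 32.
- Lag after the patient's own Cycle 2 Day 1 visit: 7 days.
- Lag after the patient's Day 21: 29 − 21 = 8 days, up to 32 − 21 = 11 days.

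**Stage 2 cohort with the 14-day stagger** (Synopsis, Section 3, 6.2.3). Count calendar days from the 1st patient's first dose (day 0), with patients 2 and 3 both dosed on day 14. Assignment falls on the 3rd patient's Day 21: 14 + 20 = day 34.

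| Patient | Skip declared (calendar day) | Relative to assignment on day 34 |
|---|---|---|
| 1st | 28 to 31 | 3 to 6 days before |
| 2nd | 42 to 45 | 8 to 11 days after |
| 3rd | 42 to 45 | 8 to 11 days after |

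If the 3rd patient enters d days after the 2nd, the 2nd patient's lag shrinks to (8 to 11) − d. At d = 7 it is still 1 to 4 days late; it is never late once d reaches 11. The 3rd patient's lag does not change. If assignment instead waited for the 3rd patient's Cycle 2 Day 1 visit, that patient's skip would still come 7 days later.

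**Stage 1 Step 1.** The next patient may be dosed from calendar day 21. The skip is known on day 28 to 31, which is 7 to 10 days later.

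**Patients exposed meanwhile.** In Step 1 the patient after that cannot be dosed before day 42, so at most one patient is treated before the skip is known. In Stage 2 the new cohort's own stagger puts its 2nd patient at least 14 days after its 1st. The lag of 8 to 11 days is shorter, so again at most one patient is dosed, although the dose has been assigned for all three.

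**Chance of a late DLT per Stage 2 cohort.** The documents give no skip rate. If a share q of patients skip for sub-threshold toxicity, the chance of at least one among patients 2 and 3 is 1 − (1 − q)². For assumed q of 2%, 5% and 10% this is 4.0%, 9.8% and 19.0%. For comparison, Table 2's Expected scenario puts the rate of all DLTs at DL4 at 7%.

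**Would one DLT move the dose?** Section 13.3 defers the skeleton to Stage 2, so four were assumed for doses −1 to 4: (0.05, 0.10, 0.25, 0.40, 0.55), (0.084, 0.157, 0.25, 0.355, 0.46), (0.036, 0.084, 0.157, 0.25, 0.355) and (0.012, 0.036, 0.084, 0.157, 0.25). The model is a power model with normal prior variance 1.34, a plug-in posterior mean and target 0.25, choosing the dose closest to target.

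| History | CRM dose under the four skeletons |
|---|---|
| 0/1 at DL1–DL3, first DLT in 1st DL4 patient | DL3 in all four |
| same, in 2nd | DL3 in three, DL4 in one |
| same, in 3rd | DL3 in one, DL4 in three |
| same, in 4th to 9th | DL4 in all four |
| 0/3 at DL1–DL3, first DLT in any of 9 DL4 patients | DL4 in all four |
| 0/1 at DL1–DL3, second DLT among 4 or 5 at DL4 | moves from DL4 to DL3 in all four |
| same, among 6 | moves to DL3 in two |
| same, among 7 to 9 | no move |

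**The case against.** The strongest reply is that the 21-day intervals are minimums and the Section 11.4 review is set as a minimum too. The team, with the statistician, confirms the timing of the next cohort and would see that a patient is on hold. This stands as a statement of what the team may do. It does not supply a rule, and the Stage 2 trigger as written is Day 21.

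A second reply is that Cycle 2 Day 1 might move with a hold and so keep the DLT period open. Section 6.1.1 resets the calendar when a held dose is given, Section 8 sets toxicity delays apart from scheduling windows, and the 10.2 table records events until the DLT assessment is completed. None of these settles the skip branch. The Schema and 8.1 tie Cycle 2 Day 1 to Day 22, 6.3 allows only three more days, and an open DLT period would still not move the Day 21 trigger.

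Three stronger readings are tempting but not supported:

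- A reader might infer that any Cycle 2 dose given after a hold has uncertain DLT status. A patient dosed by the end of the one-week hold has received Cycle 2, so this criterion is not met. Only a later dose with no declared skip is unclassified, and 6.1.1 provides no path to one.
- A reader might infer that every skip misses the cohort decision. With the stagger, the 1st Stage 2 patient's does not.
- A reader might take the permissive skip as leave to dose through a listed contraindication. Section 6.1.1 already requires those to be ruled out before any dose.

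**Conclusion.** The timing gap holds. A DLT that the plan requires can be declared 8 to 11 days after the patient's Day 21. In Stage 2 that is too late for the next assignment when it comes from the 3rd patient, and usually when it comes from the 2nd. In Stage 1 Step 1 it can come after the next patient has been dosed. The missing limit on a late, off-scheme Cycle 2 dose is real but minor.

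The day counts rest on the documents alone and assume that the full one-week hold is used. How often this happens, and what it does to the MTD, cannot be determined. The events may be uncommon: Section 7.1 reports self-limited rashes with subcutaneous delivery of the related IL-15 complex, and an improving injection-site reaction does not bar dosing. The Revision History reports no DLTs from DL1 to DL4, so the early-DL4 case in which one event most readily moves the dose may have passed. It would go too far to conclude that the MTD will be wrong. Under the assumed skeletons a single DLT often leaves DL4 in place; a second among 4 or 5 DL4 patients, after 0/1 at DL1–DL3, does not. The change is still worth making, because at present following the plan exactly can set a dose without an event the plan counts.

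**What to change.** In 6.2, 6.3 and 13.1, state that when Cycle 2 is held for treatment-related toxicity, that patient's DLT period stays open, and the next cohort or dose decision waits, until Cycle 2 is given or the one-week hold ends (Day 29, or Day 32 if the +3-day window was used).

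In 6.1.1, 6.3 and the Schema, state that Cycle 2 not given by the end of that hold because of treatment-related toxicity is a DLT, whatever is done later, and that a dose given by the end of the hold is not a DLT under this criterion.

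The cost is wording only, with no new data. A held patient may delay the next cohort by about 7 to 10 days (Day 22 to Day 29 or 32), and an occasional off-scheme late dose becomes a DLT, which could lower the selected dose. Whether to hold for a toxicity not on the contraindication list remains a clinical judgement.

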# 6.1.2 Pre Medication

Use of pre-medications is at the discretion of the treating physician on an individual patient basis. Acetaminophen may be given prior to the injection to reduce the intensity of the fever that often occurs a few hours later.

The HCW9218 intervention guidelines described below may be implemented or modified by the Investigator as medically necessary or as appropriate without requiring a protocol amendment or being considered a protocol deviation.

### **HCW9218 Intervention Guidelines**

Condition	Agents	Dose	Route	When
Fever/Chills	Antipyretic*			
	Acetaminophen	up to 650 mg; or 10 to 15 mg/kg recipient weight	Orally	Prior to each dose & repeat 4 hours after dosing prn. Repeat every 4-6 hours if fever present.
	Ibuprofen	up to 400 mg; or 10 mg/kg recipient weight	Orally	Prior to each dose & repeat 4 hours after dosing prn. Repeat every 4-6 hours if fever present
	Naproxen	up to 440 mg	Orally	Prior to each dose & repeat 8 hours after dosing prn. Repeat every 8-12 hours if fever present.

\*Antipyretic medication including acetaminophen, ibuprofen, or naproxen may be given per physician discretion following the recommended dosing thresholds:

Acetaminophen: not to exceed 3000 mg (3 grams) in 24 hours

Ibuprofen: not to exceed 2400 mg in 24 hours Naproxen: not to exceed 1100 mg in 24 hours

H1 and H2 blockers may be given prior to administration of HCW9218 per Investigator's discretion and/or Institution's standard of care related to protein-based therapeutics.

# 6.1.3 Patient Monitoring Day of HCW9218 Dosing

For Cycle 1 participants are observed for a minimum of 6 hours after HCW9218 dosing for immediate adverse events.

For Cycle 2 participants are observed for a minimum of 3 hours after HCW9218 dosing for immediate adverse events. Vital signs (body temperature, heart rate, respiratory rate, systolic and diastolic blood pressure) are documented prior to each HCW9218 dose and then after dosing at 15 minutes (±5 min), 30 minutes (± 5 min), 60 minutes (±10 min) and 120 minutes (±15 min) minutes then hourly (±15 min) until discharge from the clinic.

In addition, during Cycle 1 only, the targeted toxicity worksheet is completed as detailed in Section 10.2.2.

For subsequent doses (i.e., Cycle 3 and subsequent cycles), if the participant did not experience any severe side effects from the previous doses, they may be discharged from the treatment center 30 minutes after the HCW9218 injection at the discretion of the treating Investigator. Vital signs (body temperature, heart rate, respiratory rate, systolic and diastolic blood pressure) are documented prior to each HCW9218 dose and then after dosing at 15 minutes (±5 min) and at 30 minutes (±5 min).

# 6.1.4 HCW9218 Dosing Delay and Discontinuation

No dose reductions are permitted (except for HCW9218 dose recalculation for weight change in Section 6.1).

A dose delay is permitted per Section 6.1.1.

All attempts should be made to stay within the allotted timeframes although altering the schedule, if determined to be medically necessary by the Investigator, will not be a protocol deviation.

# 6.2 HCW9218 Dose Finding Enrollment Plan

Dose limiting Toxicity (DLT) is defined in Section 6.3.

# 6.2.1 STAGE 1 STEP 1 - Fast-track design (1 patient per dose level)

Start at DL1, enroll 1 patient per DL separated by a minimum of 21 days (DLT period) until the:

- 1st pre-defined adverse event Any of the following treatment emergent Grade 2 events lasting >72 hours within 5 days of 1st dose of HCW9218: fatigue, flu-like symptoms or injection site reaction.
- And the patient completes the 21 day DLT period with no DLT- Activate
   Stage 1 Step 2 in Section 6.2.2.

OR

1st DLT event within 21 days after the 1st dose of HCW9218 - Activate
 Stage 2 in Section 6.2.3 - Stage 1 Step 2 is not used.

OR

• 9 patients are treated at the DL4 - This completes enrollment - Stage 1 Step 2 and Stage 2 are not used.

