### STAGE 1 STEP 1 Fast-track design (1 patient per dose level)

Start at DL1, enroll 1 patient per DL separated by a minimum of 21 days (DLT period) until the:

- 1st pre-defined adverse event defined as any of the following treatment emergent Grade 2 events lasting >72 hours within 5 days of 1st dose of HCW9218: fatigue, flu-like symptoms or injection site reaction
- and the patient completes the 21 day DLT period with no DLT- Activate Stage 1 Step 2
- 1st DLT event within 21 days after the 1st dose of HCW9218 as defined in the Schema and in Section 6.3 Activate Stage 2 (Stage 1 Step 2 is not used)

  OR
- 9 patients are treated at the DL4 (This completes enrollment Stage 1 Step 2 and Stage 2 are not used)

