# **Study Schema**

1 cycle = 3 weeks (21 days) with a 2-cycle minimum unless medically contraindicated.

**HCW9218** at assigned dose by subcutaneous (SC) injection once every 3 weeks until disease progression, unacceptable toxicity, patient refusal, or felt to be no longer of benefit

Assess for Dose Limiting Toxicity (DLT) at Cycle 2 Day 1 (defined below and in Section 6.3)

tumor biopsy (baseline and prior to Cycle 3) – optional, in participants with accessible tumor who have signed the separate biopsy consent (Tumor used for biopsy should not be a RECIST target lesions unless there are no other lesions suitable for biopsy.)

Disease reassessment per disease specific standard of care (i.e. every 8-12 weeks)

Phase I HCW9218 Dose Levels			
Dose Level (DL)	HCW9218 dose		
-1*	0.1 mg/kg		
1 (start)	0.25 mg/kg		
2	0.5 mg/kg		
3	0.8 mg/kg		
4	1.2 mg/kg		

\* use only if excessive toxicity encountered at DL1

**Dose limiting toxicity (DLT)** is defined as any of the following **treatment emergent events** based on CTCAE v5 within 21 days after the 1st dose of HCW9218 as assessed on Day 22 (Cycle 2 Day 1) per Section 6.3.

DLT event	Exceptions:			
Any Grade 4 hematologic event	
 
Grade 4 lymphopenia that resolves to Grade 1 or lower (or to Baseline or lower, if pre-existing Grade 2 or higher) within 7 days
 
Grade 4 leukopenia that resolves to Grade 1 or lower (or to Baseline or lower, if pre-existing Grade 2 or higher) within 7 days
 
			
Any Grade 3 or Grade 4 febrile neutropenia				
Any Grade 3 thrombocytopenia with bleeding				
Any Grade 3 or higher non-hematologic adverse event	
 
Grade 3 nausea, vomiting and/or diarrhea that last < 72 hours
 
Grade 3 or higher electrolyte abnormality that lasts < 72 hours, is not clinically complicated, and resolves spontaneously or responds to conventional medical interventions
 
Isolated Grade 3 elevation of ALT and/or AST that resolves to Grade 1 or lower (or to Baseline or lower, if pre-existing Grade 2 or higher) within 7 days
 
Grade 3 amylase or lipase that is not associated with symptoms or clinical manifestations of pancreatitis
 
Grade 3 fatigue, not due to disease progression, that lasts < 1 week
 
			

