# 6.2.2 STAGE 1 STEP 2 - Expand Current and Future DLs to 3 Patients

The cohort size increases from 1 to 3 patients with 2 additional patients added to the current cohort. A minimum of 21 days must separate each dose cohort. Continue dose escalation until:

- 1st DLT event Activate Stage 2 in Section 6.2.3.

  OR
- 9 patients are treated at the DL4 This completes enrollment and Stage 2 is not used.

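### In Stage 1 Step 1, Grade 3 fatigue lasting more than 72 hours but under 7 days inside the trigger window is neither a cohort-expansion trigger nor a DLT, although Grade 2 fatigue of the same length expands cohorts to three

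*Combined protocol and SAP*

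**What the plan says.** **Expansion trigger.** The Synopsis (Stage 1 Step 1) counts "any of the following treatment emergent Grade 2 events lasting >72 hours within 5 days of 1st dose of HCW9218". Section 6.2.1 uses the same terms: "treatment emergent Grade 2 events lasting >72 hours within 5 days of 1st dose of HCW9218: fatigue, flu-like symptoms or injection site reaction". The patient must also finish the 21-day DLT period without a DLT. The consequence, in Section 6.2.2, is: "The cohort size increases from 1 to 3 patients with 2 additional patients added to the current cohort". Later levels also take three.

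**DLT.** The DLT tables in Section 6.3 and the Study Schema include "Any Grade 3 or higher non-hematologic adverse event". Both list as an exception "Grade 3 fatigue, not due to disease progression, that lasts" less than 1 week. A separate row makes a DLT of "Inability to receive Cycle 2 dosing due to treatment related toxicity". In Step 1, the "1st DLT event within 21 days after the 1st dose of HCW9218" opens Stage 2 directly.

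**Scope.** Section 6.3 says that, in the fast-track phase only, "patients also are monitored for the pre-defined treatment emergent events defined in Section 6.2.1". It adds no trigger for a Grade 3 event that is not a DLT.

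**Other descriptions of the trigger.** Section 13.1 refers to Section 6.2.1 but gives a window of 21 days, not 5. Footnote 1 to Table 2 (Section 13.3) says that SAEs without a DLT open Step 2.

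**The concern.** An escalation rule should not respond less to a worse event. Here the trigger names Grade 2 alone and the DLT table excuses short Grade 3 fatigue. A band of Grade 3 fatigue therefore falls between the two rules, while Grade 2 fatigue of the same duration is caught.

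In Step 1 the pre-defined event is the only written rule, short of a DLT, that enlarges a one-patient cohort in the operative sections. The drug had not been given to humans when the background was written (Sections 2.2.3 and 7.1). Fatigue is a foreseeable toxicity: Section 7.2 lists it as common for similar drugs, and Appendix II marks it for all three related classes. What is at stake is whether a stronger early signal leaves the next dose level opening on one patient, when a weaker signal would have added patients first.

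**Working it through.** The plan gives no figure for this point, so the check applies the two rules side by side.

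**Inputs**
- Trigger (Synopsis, 6.2.1): Grade 2, more than 72 hours, within 5 days of dose 1.
- DLT (Schema, 6.3): Grade 3 or higher non-hematologic, except Grade 3 fatigue not due to progression lasting less than 1 week.
- Severity order (Appendix IV): Grade 2 fatigue limits instrumental activities of daily living; Grade 3 limits self-care.

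**Step 1. Literal result for fatigue.** Assume the event is inside the trigger window, is not due to progression and does not prevent Cycle 2.

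| Duration | Grade 2 | Grade 3 |
|---|---|---|
| 3 days or less | no action | no action |
| more than 3, under 7 days | Step 2 (cohorts of 3) | no action (next level, 1 patient) |
| 7 days or more | Step 2 | DLT, Stage 2 |

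Only the middle row is out of order. Grade 2 fatigue for 4 days expands cohorts, Grade 3 fatigue for 5 days does not, and Grade 3 fatigue for 8 days opens Stage 2.

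**Step 2. The other listed events.** Flu-like symptoms and injection site reaction have no Grade 3 exception, so at Grade 3 they are DLTs. The gap is specific to fatigue.

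**Step 3. The window.** The inversion exists only where Grade 2 fatigue would itself have counted. With a 5-day window this means onset by Day 5, or within about 5 − 3 = 2 days of dosing if the full 72 hours must fall inside it; the text does not say which. Under the 21-day window in Section 13.1 the gap would be wider.

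**Step 4. Effect on enrollment, extreme case.** Suppose the event occurs at DL1 and no later trigger or DLT follows.
- Literal rule: 1 + 1 + 1 = 3 patients before DL4, and 3 + 9 = 12 in total.
- If it had counted as a trigger: 3 + 3 + 3 = 9 before DL4, and 9 + 9 = 18 in total.
- Difference: 9 − 3 = 6 patients. DL4 takes 9 either way.

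**Step 5. What the extra patients would show.** The chance of at least one DLT among n patients is 1 − (1 − p)^n. With the excessive-toxicity DLT rates of Table 2:
- DL1, p = 10%: the first patient has already cleared the DLT period, so the gain comes from two patients: 1 − 0.90² = 19.0%, against no further patients.
- DL2, p = 25%: one patient 25.0%; three patients 1 − 0.75³ = 57.8%.
- DL3, p = 40%: one patient 40.0%; three patients 1 − 0.60³ = 78.4%.

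These figures show what cohort size is worth under a pessimistic scenario. They do not say how often the gap would be met.

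**Step 6. Effect of closing the gap.** If listed non-DLT events above Grade 2 received at least the Grade 2 response, the only cell of the table to change would be Grade 3, more than 3 and under 7 days.

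**The case against.** **Grade 2 may be meant as a minimum.** A study team might well read it so, or might count a Grade 3 episode that later sits at Grade 2 for more than 72 hours. The protocol states neither. It writes at-least wording where it means it, for example in the AE documentation table of Section 10.2 and the DLT table of Section 6.3. The worksheet in Section 10.2.2 records the highest grade since the last assessment, so such an episode would appear as Grade 3.

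**Other safeguards exist.** A reader might infer that nothing else restrains one-patient escalation. That goes too far. Section 11.4 requires a review of each patient after the first 21 days to confirm the timing and dose level of the next cohort, and Section 11.3 provides quarterly DSMC review. Fatigue that prevented Cycle 2 would be a DLT, though fatigue resolved within a week would not normally do so. A serious episode would open Step 2 under the Table 2 footnote. None of these is a stated rule in the operative sections for enlarging the cohort, so the gap stands with its importance reduced.

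**The gap is narrower than it looks.** A reader might take it to cover all Grade 3 fatigue of 3 to 7 days in the DLT period. Under the 5-day window of Section 6.2.1 it does not: fatigue starting on Day 8 triggers Step 2 at neither grade.

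**Escalation may be over.** The Revision 3 entry (March 29 2023) reports no DLTs from dose level 1 to dose level 4. DL4 is the top level and takes 9 patients under either step, so the forward effect is probably small. This objection largely stands. It does not show that the gap was never met, since events in it are by definition not DLTs; nor do the documents show that it was met.

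**Conclusion.** The inconsistency is real on the current text. In Step 1, within the trigger window, Grade 3 fatigue lasting more than 72 hours but under 7 days, not due to progression and not preventing Cycle 2, receives a weaker enrollment response than Grade 2 fatigue of the same length. The largest consequence is 3 rather than 9 patients treated before DL4, which assumes the event falls at DL1 and no later trigger or DLT occurs.

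The probability of meeting the gap cannot be computed, because the documents give neither the frequency nor the duration of such fatigue; any percentage would rest on an assumed distribution. The finding does not show that escalation in this trial was unsafe. It is a wording defect in a decision rule, worth correcting because the rule gives a perverse result in a first-in-human escalation and the correction is cheap.

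**What to change.** Reconcile the trigger in the Synopsis and Section 6.2.1 with the fatigue exception in the Study Schema and Section 6.3. The principle is that a listed event that is not a DLT should not receive a weaker enrollment response than a lower-grade event of the same kind and duration. The sponsor and investigator choose the threshold.

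In the same edit:
- Settle the window, 5 days in Section 6.2.1 against 21 days in Section 13.1, and say whether onset or the full 72 hours must fall inside it.
- Align footnote 1 to Table 2, which names SAEs, with the Section 6.2.1 list, and confirm which trigger the simulations used. A wider trigger may change the event rates assumed there.
- State how an episode that changes grade is counted.

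The cost is a few lines of text and a check of Table 2. If the trigger then fires at DL1, up to 6 more patients are treated below DL4 (9 rather than 3), giving 18 in total with 9 at DL4, within the maximum of 24, plus the time to enroll and observe them.
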